**Figure 3.1.1-1: Dose Escalation Algorithm**

a Treat 2 subjects initially if no DLTs in Dose Level 1 and criteria for transitioning from 100% increment to Fibonacci is not met; treat 3 to 4 subjects initially, otherwise.

b At the same dose, decision making based on other combinations of k/n are shown in [Appendix 1](#).

c Treat the next cohort of subjects at the next higher dose.

d Treat 3 more subjects at the current dose.

e Treat 3 more subjects at the next lower dose.

f Unacceptable current dose. Do not re-escalate to this dose.

DLT: dose-limiting toxicity; k: cumulative number of subjects who experienced DLT; MTD: maximum tolerated dose; n: cumulative number of DLT evaluable subjects; QW: every week; Q3W: every 3 weeks.

### Part 1A: Maximum Tolerated Dose Determination

At the end of dose escalation, the MTD will be selected as the dose with the smaller difference of estimated toxicity and the target DLT rate (27%), among the doses used, with isotonic regression modeling of the accumulated DLT data based on the mTPI design.

### **Part 1B: BMS-986148 Administered QW for 3 Weeks and 1 Week Off**

Approximately 24 subjects will be enrolled in ascending dose cohorts. Part 1B may begin after determining the MTD or a tolerated dose below the MTD in Part 1A. The starting dose for Part 1B will be chosen by modeling active ADC concentration-time data from Part 1A and selecting a fractionated dose that provides similar exposure to that of the MTD or a tolerated dose below the MTD. In the event that concentration-time data are not available for modeling, the starting dose will be 1/3rd of the MTD or a tolerated dose below the MTD from Part 1A. In Part 1B, BMS-986148 is administered every week for 3 weeks and 1 week off in a 28 day cycle.

### **Part 1B: Selection of Doses**

Similar to dose selection in Part 1A, a modified Fibonacci dose escalation will be used. Dose escalation for each subsequent cohort of subjects will be guided by the incidence of BMS-986148-related AEs as graded by NCI CTCAE v4.03 in the first 4 weeks of dosing (DLT evaluation period). Dose escalation will be in increments of 100% above the previous dose level until the first occurrence of any of the following: DLT,  $\geq$  Grade 3 decrease in neutrophil count lasting  $> 72$  hours,  $\geq$  Grade 3 thrombocytopenia lasting for  $> 72$  hours,  $\geq$  Grade 2 ocular toxicity, or 2 subjects with  $\geq$  Grade 2 AEs in a single dose level cohort and considered related to BMS-986148 with the following exceptions: asymptomatic electrolyte abnormalities that can be managed with appropriate supplements and Grade 2 alopecia. In addition, Grade 2 fatigue that is less than 2 grades from baseline (ie, from Grade 1 to Grade 2) will not trigger a Fibonacci sequence. Once one or more of the above occur, a modified Fibonacci dose escalation will be employed for any subsequent dose escalations, with increments of 67%, 50%, 40%, and 33%. Any further dose escalations will be 33%.

Intermediate doses may be evaluated if agreed upon by the BMS Medical Monitor and investigators. The next dose level will not exceed 100% or the dose increment per the modified Fibonacci dose escalation.

### **Part 1B: Dose Escalation Decision Rules**

The same mTPI design (Figure 3.1.1-1 and Appendix 1) as in Part 1A will be used to help guide escalation decisions except that all dose levels in Part 1B begin with an initial number of 3 to 4 subjects. A fourth subject may be enrolled in a dose escalation cohort following agreement between the investigator and the BMS Medical Monitor if able to start the first day of dosing within approximately 1 week of the third subject in the same dose escalation cohort. The DLT evaluation period will be 28 days. At least 3 DLT-evaluable subjects treated at each of the dose levels in Part 1B will be required to enable a decision to escalate, add more subjects to the current dose level, or de-escalate. Subjects must receive 3 doses in Part 1B during the DLT evaluation period (unless DLT has occurred) to be considered evaluable for dose escalation decisions. Subjects with insufficient data to establish safety during the DLT evaluation period at the dose tested (eg, omitted or reduced doses for reasons other than a DLT) may be replaced upon agreement of the BMS Medical Monitor and investigators.

### **Part 1B: Maximum Tolerated Dose Determination**

Similar to the MTD determination in Part 1A, at the end of dose escalation, the MTD will be selected as the dose with the smallest difference of estimated toxicity and the target DLT rate (27%), among the doses used. See Section 4.5.1 for more information about DLTs.

Once the safety (during DLT evaluation) of a dose level has been established (Part 1A and/or Part 1B), additional subjects may be added at that dose to better characterize the PK, safety, and PD profile.

#### **3.1.2 Dose Expansion (Part 2)**

The purpose of the cohort expansion will be to assess preliminary antitumor efficacy, expanded safety experience, and PD effects of BMS-986148. Additional subjects will be treated after the completion of Part 1A and/ or Part 1B, at the MTD, or at an alternative dose below MTD as agreed upon by the BMS Medical Monitor and investigators. Part 2 can begin before the completion of Part 1B as the Q3W dosing regimen is the intended regimen for Part 2. However, if the aggregate PK and safety data indicate similar safety but higher cumulative exposure with the QW dose schedule, this schedule may also be evaluated in Part 2 in an additional cohort of 25 to 26 subjects, once the MTD or a tolerated dose below the MTD is identified in Part 1B. Treatment doses in the cohort expansion groups will not exceed the MTD.

Five expansion cohorts will be restricted to these tumor types 1) mesothelioma 2) pancreatic 3) ovarian 4) NSCLC, and 5) gastric cancer. Enrollment in cohort expansion will be determined by the mesothelin expression of the archived tumor sample (or fresh tumor sample if archived sample is not available).

The enrollment in each expansion cohort will be guided by a Simon 2-Stage design framework (see [Table 8.1-1](#)) exploring efficacy in the following 2 populations: [REDACTED]

Anti-tumor activity will be assessed initially in approximately 12 to 15 evaluable subjects per tumor type (Stage 1) treated in each monotherapy cohort, with the option to stop enrolling in a cohort without an initial anti-tumor activity signal. The number of subjects needed for the Stage 1 review is guided by a Simon 2-Stage design as shown in Table 8.1-1 below for each tumor type with futility boundaries as follows: after Stage 1, if none of the first 15 evaluable subjects in the gastric or pancreatic cohorts, if  $\leq 2$  of the first 12 with mesothelioma, or  $\leq 1$  of the first 14 with NSCLC or ovarian cohort demonstrate clinical activity, enrollment in the cohort meeting criteria may be stopped for this population.

Evaluation of efficacy will occur independently in each tumor cohort. At the time of the Stage 1 efficacy assessment, [REDACTED] to allow an initial efficacy assessment in both the [REDACTED] populations. If there is a lack of signal for preliminary efficacy (number of responders not exceeding the boundary), and after evaluation of all available data, enrollment may be stopped in that population. Otherwise, additional subjects will be treated in Stage 2 for the population in which there was an initial signal. [REDACTED]

Of note, fresh tumor biopsy at screening and on treatment will be mandatory for 10 ovarian cancer subjects and 10 gastric cancer subjects enrolled in Part 2. Fresh tumor biopsy at screening and on treatment will be optional for subjects with other indications. [REDACTED]

As the expected time of response relative to dose initiation and the actual recruitment rate are unknown, it is expected that during the efficacy evaluation of subjects in Stage 1, additional subjects may have been enrolled and will be receiving treatment than the minimum needed for the Stage 1 assessment. Therefore, the above numbers are approximate, and enrollment may continue during the evaluation of the interim data.

Safety monitoring of subjects enrolled in the Part 2 (Phase 2a) portion of the study will be the same as that conducted during the dose escalation portion. During Part 2, if in a given arm the combined incidence of study drug-related AEs that require dose modification exceeds 29% (of treated subjects), then further enrollment to that arm will be interrupted, and the findings will be discussed between the BMS Medical Monitor and investigators. An agreement will be reached as to whether a lower dose or an alternate dose schedule of BMS-986148 should be examined or whether any additional treatment guidelines should be implemented prior to enrollment of additional subjects on study.

### **3.1.3 BMS-986148 in Combination with Nivolumab (Part 3)**

During the dose escalation phase with BMS-986148 and nivolumab combination therapy (Part 3A), approximately 12 evaluable subjects are expected to be treated at 2 doses of BMS-986148 (0.8 mg/kg and 1.2 mg/kg Q3W) and nivolumab (360 mg Q3W) combination therapy. In the BMS-986148 and nivolumab combination therapy dose expansion phase (Part 3B), approximately 25 to 26 evaluable subjects will be treated at each tumor cohort.

#### **3.1.3.1 Part 3A (Dose Escalation)**

##### **Selection of Dose Levels to be Evaluated**

The starting dose of BMS-986148 to be combined with nivolumab at 360 mg Q3W in Part 3A will be 0.8 mg/kg administered IV Q3W.

Approximately 12 subjects will be enrolled in ascending dose cohorts starting with a dose of BMS-986148 (0.8 mg/kg IV Q3W, first dose level) with nivolumab 360 mg administered Q3W in a 21-day cycle. Subsequent escalation to 1.2 mg/kg Q3W of BMS-986148 (or MTD determined from Part 1A) in combination with nivolumab 360 mg Q3W will be guided by the mTPI design described below. In the event that the first dose level of BMS-986148 is determined to exceed the MTD in combination with 360 mg Q3W of nivolumab, a lower BMS-986148 dose tested in monotherapy escalation (such as 0.4 mg/kg and/or 0.2 mg/kg) may be explored based on available safety, PK [REDACTED]. Nivolumab will be administered as 360 mg IV Q3W in all dose cohorts.

Intermediate doses of BMS-986148 in combination with 360 mg Q3W of nivolumab may be evaluated if agreed upon by the BMS Medical Monitor and investigators. The next dose level will not exceed 100% of the dose increment.

##### **Dose Escalation Decision Rules**

A similar mTPI design as in Part 1A will be used to guide dose escalation decisions and to select the MTD. A DLT target rate of 29% (EI = 28% to 31%) will be utilized for combination treatment to guide escalation decisions. Dose escalation decisions will be based on the total number of subjects in a dose level who were DLT evaluable and the number of DLTs, guided by the mTPI Bayesian model and posterior inference.

The number of subjects at the initial cohort of all dose levels in Part 3A will be 3 to 4. A fourth subject may be enrolled in a dose escalation cohort following agreement between the investigator and the BMS Medical Monitor if able to start the first day of dosing within approximately

1 week of the third subject in the same dose escalation cohort. The DLT evaluation period will be 21 days. Enrollment of additional cohorts at the same dose level will proceed in sample sizes of up to 3 or 4 subjects. Subsequent dose levels will follow similar cohort enrollment size and decision rules. At least 3 DLT-evaluable subjects treated at each of the dose levels in Part 3A will be required to enable a decision to escalate, add more subjects to the current dose level, or de-escalate and declare the current dose as unacceptable (exceeding the MTD). Subjects with insufficient data to establish safety during the DLT evaluation period at the dose tested (eg, omitted or reduced doses for reasons other than a DLT) may be replaced upon agreement of the BMS Medical Monitor and investigators.

**Table 3.1.3.1-1: Dose Escalation Decision Guide in Combination with Nivolumab**

		Number of DLT Evaluable Subjects at a Dose Level									
		3	4	5	6	7	8	9	10	11	12
N of DLT at a dose level	0	E	E	E	E	E	E	E	E	E	E
	1	S	S	S	E	E	E	E	E	E	E
	2	D	S	S	E	S	S	S	S	E	E
	3	DU	DU	D	E	S	S	S	S	S	S
	4		DU	DU	DU	D	D	S	S	S	S
	5			DU	DU	DU	DU	DU	D	S	S
	6				DU	DU	DU	DU	DU	DU	D
	7					DU	DU	DU	DU	DU	DU
	8						DU	DU	DU	DU	DU
	9							DU	DU	DU	DU
	10								DU	DU	DU
	11									DU	DU
12										DU	

DLT: dose-limiting toxicity; E: escalate to next higher dose level; D: de-escalate to the next lower dose level; S: stay at the current dose level; DU: unacceptable dose level, not to be re-visited.

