## **APPENDIX 2            SIMULATIONS OF MTPI VS 3 + 3 DOSE ESCALATION DESIGNS**

### **1                    SIMULATIONS FOR MONOTHERAPY DOSE ESCALATION, WITH 6 DOSE LEVELS**

Simulations of mTPI and 3+3 designs, as shown below, demonstrate that the mTPI design has a greater chance of selecting the correct MTD than the 3+3 design, and treating fewer subjects at sub-optimal doses.

The mTPI uses a set of decision rules guided by simple Bayesian models and requires a clinically relevant pre-determined target DLT rate and an equivalence interval (EI), within which any dose is considered close to the true maximum tolerated dose (MTD). For this study, the selected target toxicity (DLT) rate is 27% and EI [25%, 29%].

The mTPI design makes decisions using the same two observed numbers as the traditional 3+3 design, the number of DLT evaluable subjects and the number of subjects with DLT. Based on these two numbers, unit probability mass is calculated within each of three regions as stated above, and decision is based on which region has the largest unit probability mass:

- E: escalating to the higher dose if interval (0, 25%) has the largest unit probability mass,
- S: staying at the same dose if interval [25, 29%] has the largest unit probability mass,
- D: de-escalating to the lower dose if interval (29, 100%) has the largest unit probability mass.

At the end of the trial, MTD will be picked, by isotonic regression estimation method, to be the dose whose estimated toxicity rate is closest to the target toxicity rate among all the tried doses.

Simulations were performed to examine the performances of mTPI and 3 + 3 design for this study. Escalation decisions based on the mTPI are shown in the protocol. Decisions based on the 3+3 design are shown below:

- E: no subject with DLT out of 3 DLT evaluable subjects initially, or at most 1 subject with DLT out of 6 DLT evaluable subjects after adding 3 more subjects.
- S: 1 subject with DLT out of 3 DLT evaluable subjects initially.
- D: at least 2 subjects with DLT out of 3 DLT evaluable subjects initially, or at least 2 subjects with DLT out of 6 DLT evaluable subjects after adding 3 more subjects

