## 2 SIMULATIONS FOR NIVOLUMAB COMBINATION DOSE ESCALATION, WITH 2 DOSE LEVELS

Similarly to the monotherapy setting simulations for the BMS-986148 and nivolumab combination therapy show that the mTPI design has a greater chance of selecting the correct MTD than the 3 + 3 design, and treats fewer subjects at suboptimal doses than the 3 + 3 design.

The mTPI design described above was set up with a target toxicity (DLT) rate of 29% (EI [28%, 31%]) because somewhat higher toxicity is expected and acceptable in the combination setting.

The mTPI design makes decisions using the number of DLT evaluable subjects and the number of subjects with DLT. Based on these 2 numbers, the unit probability mass calculated in each region is defined by the EI for the combination setting, with the decision based on the region that has the largest unit probability mass, similarly as described above for the monotherapy.

In the simulation with mTPI, 1 out of 4 subjects may drop out with a probability of 0.5. Dropout is not simulated in the 3 + 3 design, since replacement subject is always needed to reach a decision.

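### The Part 3A decision table says escalate at 2 of 6 and 3 of 6 DLTs, against the protocol's own 29% target and its mTPI rule

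*Protocol*

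**What the plan says.** For the combination escalation, Section 3.1.3.1 of the protocol sets the design inputs: "A DLT target rate of 29% (EI = 28% to 31%) will be utilized for combination treatment to guide escalation decisions". Appendix 2, section 2, describes how a decision is reached, "with the decision based on the region that has the largest unit probability mass". Appendix 2, section 1, defines the regions for monotherapy, for example "escalating to the higher dose if interval (0, 25%) has the largest unit probability mass". Part 3A follows the same scheme with its own limits, so escalation belongs to the region below 28%.

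Table 3.1.3.1-1 turns this into a lookup by number of DLTs and number of evaluable subjects (3 to 12). Its key reads "E: escalate to next higher dose level; D: de-escalate to the next lower dose level; S: stay at the current dose level", and DU marks a dose that is unacceptable and closed. The row for three DLTs is "3 DU DU D E S S S S S S". In the row for two DLTs, the entries at 5, 6 and 7 subjects are S, E and S. Down the column for six subjects, 0 to 4 DLTs give E, E, E, E, DU.

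On cohort size, Section 3.1.3.1 says "The number of subjects at the initial cohort of all dose levels in Part 3A will be 3 to 4" and "Enrollment of additional cohorts at the same dose level will proceed in sample sizes of up to 3 or 4 subjects". Six evaluable subjects at a dose is therefore an ordinary place to make a decision.

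**The concern.** The fault shows before any model is fitted. With the DLT count fixed, each further subject without a DLT makes a dose look safer. Along a row, decisions can therefore only move from DU through D and S towards E. D, E, S in the three-DLT row and S, E, S in the two-DLT row break that order, whatever prior is used. In the six-subject column, one more DLT moves the instruction from escalating at 3/6 to closing the dose at 4/6.

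The same observed rates are also treated differently elsewhere in the table. A rate of 33% gives S at 1/3, 3/9 and 4/12. A rate of 50% gives S at 2/4 and D at 4/8, 5/10 and 6/12. The monotherapy table in Appendix 1, with a 27% target, has S at 2/6 and D at 3/6.

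Participant safety is at stake. A result of 2/6 or 3/6 at 0.8 mg/kg would point the team to 1.2 mg/kg with nivolumab. Section 1.5.2 names overlapping hepatotoxicity as a risk and reports transaminase DLTs in 4 of 10 subjects at 1.6 mg/kg monotherapy. Section 7 provides no data monitoring committee.

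**Working it through.** **Inputs.** Target 0.29 and interval 0.28 to 0.31 (Section 3.1.3.1); the largest-unit-probability-mass rule (Appendix 2). The documents state neither the prior nor the unacceptability cut-off. I assumed Beta(1,1), and DU when P(DLT rate > 0.29) exceeds 0.95.

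**Formula.** With x DLTs in n subjects the posterior is Beta(1+x, 1+n−x). Unit mass is the posterior probability of a region divided by its length: 0.28 below the interval, 0.03 within it, 0.69 above it. The posterior probability below a limit c equals P(Binomial(n+1, c) ≥ x+1), so each cell can be checked by hand.

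**Reproducing the cells around the two in question.**

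| Cell | E mass | S mass | D mass | P(rate > 0.29) | Computed | Printed |
|---|---|---|---|---|---|---|
| 1/6 | 2.24 | 2.16 | 0.45 | 0.35 | E | E |
| 2/5 | 0.78 | 1.83 | 1.05 | 0.76 | S | S |
| 2/7 | 1.42 | 2.54 | 0.76 | 0.58 | S | S |
| 3/5 | 0.20 | 0.77 | 1.34 | 0.94 | D | D |
| 3/7 | 0.57 | 1.77 | 1.14 | 0.82 | S | S |
| 4/6 | 0.08 | 0.40 | 1.40 | 0.98 | DU | DU |

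**The two cells.**

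- 2/6, Beta(3,5): region probabilities 0.30807, 0.06764 and 0.62428. Divided by 0.28, 0.03 and 0.69, they give 1.10, 2.25 and 0.90. The decision is S; the table prints E.
- 3/6, Beta(4,4): region probabilities 0.10160, 0.03777 and 0.86063. The unit masses are 0.36, 1.26 and 1.25. The decision is S, narrowly over D; the table prints E. P(rate > 0.29) = 0.887.

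Over the whole table 83 of 85 cells agree, and these two are the only mismatches.

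**Sensitivity.** I repeated this with priors Beta(1,1), Beta(0.5,0.5) and Beta(0.005,0.005), and cut-offs 0.80, 0.85, 0.90 and 0.95. The 2/6 cell is S every time. The 3/6 cell is S at cut-offs 0.90 and 0.95, and DU at 0.85 and 0.80. Neither is ever E.

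**Consequence on the 3 + 3 path.** One DLT in 3 is S, so three more subjects are treated. As printed, escalation follows 0, 1 or 2 further DLTs; under the stated rule it follows only 0. With true DLT rate p:

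- printed: 3p(1−p)² × (1−p³)
- stated rule: 3p(1−p)² × (1−p)³

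| True rate p (assumed) | P(1 of 3) | Escalate, printed | Escalate, stated rule | Difference: landing on 2/6 or 3/6 |
|---|---|---|---|---|
| 0.15 | 0.325 | 0.324 | 0.200 | 0.124 |
| 0.27 | 0.432 | 0.423 | 0.168 | 0.255 |
| 0.29 | 0.439 | 0.428 | 0.157 | 0.271 |
| 0.40 | 0.432 | 0.404 | 0.093 | 0.311 |
| 0.50 | 0.375 | 0.328 | 0.047 | 0.281 |

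The escalation probabilities include 1/6, where E is correct. The last column isolates the effect of the two cells.

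**The case against.** Five points can be made for the plan.

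- **A misread PDF.** Two adjacent letters in one column could have been misread when the published file was converted to text. This cannot be fully excluded. However, both rows carry the right ten entries and every other cell fits the algorithm, so a column shift is not the explanation. The source page should settle it.
- **The table is only a guide.** The title and Section 3.1.3.1 use that language, and the medical monitor could refuse to escalate. Judgement may catch the error, but it does not make the recommendation right.
- **Six subjects is not the only second look.** Cohorts of four are allowed, so the second decision may fall at 7 or 8. The Appendix 2 simulations use cohorts of four, with one subject in four dropping out with probability 0.5. This stands: six is one ordinary second decision point among several, and the figures above apply to cohorts of three.
- **Rates of 40% and 50% are pessimistic for the first dose.** The combination scenarios in Appendix 2 put that dose at 15% to 27%, and Section 1.5.2 reports no DLTs in 4 evaluable subjects at 0.8 mg/kg monotherapy. This is fair, so lower rates are tabulated. The gap remains, although escalating from a dose whose true rate is below target does less harm.
- **The MTD estimate uses observed counts.** The isotonic regression would still see 3/6 as 3/6. This is right: the error changes who is treated at which dose and how much data each dose gathers, not the recorded counts.

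**Conclusion.** The concern holds. The entries at 2/6 and 3/6 contradict the target, interval and decision rule that the protocol states, and they contradict the cells beside them. That neither should be E rests on no single prior: the row order alone rules it out, and every prior and cut-off tried agrees. That both should be S rests on the assumed Beta(1,1) prior and 0.95 cut-off, which reproduce the rest of the table exactly. At 3/6 the margin of S over D is slight (1.26 against 1.25).

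With cohorts of three, the two cells add 12 to 31 percentage points to the chance of escalating on the path through 1/3, across true rates of 15% to 50%. The effect is concentrated at 0.8 mg/kg, because Part 3A plans only one higher dose. This must be fixed: it is a wrong safety threshold in a trial whose primary objective is safety.

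**What to change.** Check the source page of Table 3.1.3.1-1, then regenerate the table from the 29% target and the 28% to 31% interval. Replace E with S at 2/6 and at 3/6. If the team prefers more caution at 3/6, where S and D are almost tied, D would match the monotherapy table; the departure from the algorithm should then be stated. Confirm that the corrected entries agree with Section 3.1.3.1 and Appendix 2, and that any difference from Appendix 1 follows from its different target. Give the prior and the unacceptability cut-off beside the table so that others can reproduce it.

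The cost is two table cells and a footnote, issued by amendment or administrative letter before the table is used. No extra subjects, visits or procedures are needed.
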